Objective 3: We will examine the impact that the intervention has on attendance at scheduled dental treatment appointments over the next 12 months.

Secondary Objectives:

We will examine whether I-CBT has similar effects on related measures (pain sensitivity, anxiety sensitivity, distress tolerance, symptoms of specific phobia of dental procedures, blood-injury-injection phobia, sleep disturbance and sleep-related impairment, functional impairment due to dental anxiety, and consumer satisfaction) at one- and three-month follow-ups.

We will also examine whether the Internet-based intervention reduces anticipated and perceived pain and anxiety during dental procedures in immediately pursuant appointments for dental treatment.

We will also examine whether baseline levels of distress tolerance and pain sensitivity moderate the efficacy of the dental anxiety intervention.

5) Rationale and Significance

Page 2 of 28 Revision: May 12, 2023

Dental anxiety (i.e., anxiety related to undergoing dental procedures) is a major public health concern, as it leads to underutilization of dental care and poor oral health. Approximately 10-20% of individuals in the US endorse significant dental anxiety, and 10-50% cancel regular dental care appointments or delay treatment for a painful dental condition due to fears of dental procedures (Sohn & Ismail, 2005). Patients with dental anxiety are more likely to be referred for nitrous oxide sedation (Boyle, Newton, & Milgrom, 2009) and use emergency dental services (Kanegane, Penha, Borsatti, & Rocha, 2003), both of which increase individual and public dental healthcare costs. Dental anxiety has been consistently associated with increased oral health problems and impairment (e.g., more cavities; Armfield, Stewart, & Spencer, 2007). Few studies have examined the efficacy of psychological treatments for dental anxiety (Gordon, [name], Tellez, & Ismail, 2013), and most of the existing empirically supported psychological interventions cannot be easily disseminated within dental healthcare settings, as they must be administered by highly trained clinicians over a number of sessions. Therefore, it is the goal of our ongoing research program to develop a brief online therapy for dental anxiety that could be easily implemented in dental clinics, allowing for broader dissemination.

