Pain Sensitivity Index (PSI; Gross, 1992a). The PSI is a 16-item self-report measure that assesses the fearful appraisal of pain and the expected physical, psychological, and social consequences of pain. Items are rated on a scale ranging from 0 (not at all) to 7 (very much) reflecting the degree to which the item applies to the respondent. Higher scores indicate higher levels of pain sensitivity. The scale has demonstrated high internal consistency in previous studies with dental patients (α = 0.92) (Klages et al., 2004). It was found to measure a construct distinct from dental phobia and health concerns (Gross, 1992a). Pain sensitivity is considered a stable characteristic that can influence the development of situational fears (Gross, 1992b). It has been related to dental anxiety and expectation of pain before dental procedures (Klages et al., 2004). The PSI will play a dual role in this study, as a secondary outcome measure and as a hypothesized moderator of the efficacy of the Internet-based dental anxiety intervention compared to the active control condition. It will be administered at baseline and the 1-month and 3-month follow-ups.

Distress Tolerance Scale (DTS; Simons & Gaher, 2005). The DTS is a 15-item self-report measure assessing one's perceived ability to experience and tolerate negative emotional states. This scale measures four dimensions of distress tolerance: subjective appraisal of distress, ability to tolerate emotional distress, absorption of attention by negative emotions, and regulation efforts to alleviate distress. Items are rated on a scale ranging from 1 (strongly agree) to 5 (strongly disagree). Total score range from 15 to 75, with higher scores reflecting higher levels of distress tolerance. This scale has high internal consistency (α = .89), appropriate convergence with other self-report ratings of affective distress and regulation, and adequate six-month test-retest reliability (r =.61). The DTS will also play a dual role in this study, as a secondary outcome measure and as a hypothesized moderator of the efficacy of the Internet-based dental anxiety intervention compared to the active control condition. It will be administered at baseline and the 1-month and 3-month follow-ups.

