Aim 1 will test the equivalence hypothesis (Ho: the two intervention conditions are not equivalent). MDAS and ADIS fear scores will be the primary outcomes to be compared between two intervention conditions for equivalence. The two one-sided tests (TOST) procedure of Schuirmann (1987) will be used to conduct the equivalence test. Linear mixed-effects models for repeated measures will be used to assess differences between intervention groups using the MDAS and ADIS fear rating as continuous outcome variables. Linear mixed-effects models will also investigate the treatment effect on dental anxiety or fear after accounting for other confounding factors. Similar analyses will be conducted for secondary outcome measures (pain sensitivity index, anxiety sensitivity index, sleep disturbance and sleep-related impairment scales, disability scale, distress tolerance scale, client satisfaction and blood-injury-injection phobia). Statistical significance will be set at p < 0.05. Multiple imputation (MI) will be used to handle missing follow-up data as described below.

Aim 1 will also determine whether the Internet-based intervention reduces dental anxiety/fear as determined by self-ratings or assessor ratings at one month and three months post-intervention. Initially, we will assess within-group change of anxiety or fear scores for each condition separately using paired *t*-tests. Linear mixed-effects models will be used to estimate within-group reduction of anxiety/fear at assessments one and three months after the administration of the intervention adjusting for other covariates.

Specific Aim 2

Aim 2 will assess the superiority hypothesis (Ho: there are no significant differences between the interventions and control). MDAS and ADIS-5 fear scores will be the primary outcomes to be compared. Initially, we will assess the differences between the interventions and control using two-sample *t*-tests. The main analysis will be based on linear mixed-effects models for repeated measures (using the MDAS score and ADIS-5 fear rating as continuous outcome variables) to assess differences between intervention and control groups. Linear mixed models will also investigate the treatment effect on dental anxiety or fear after accounting for other confounding factors. Similar analyses will be conducted for secondary outcome measures (e.g., client satisfaction and blood-

Page 17 of 28 Revision: May 12, 2023

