To determine whether primary objectives 1 and 2 are reflected in measures of other related constructs such as pain sensitivity, distress tolerance, anxiety sensitivity, and anticipated and perceived pain and anxiety, the statistical methods described above will be used. The moderating role of distress tolerance and pain sensitivity as expressed in the secondary objectives will be assessed as well. We will examine whether baseline levels of distress tolerance and pain sensitivity moderate the efficacy of the dental anxiety intervention. We will examine the moderating effect of these factors on the intervention and the reduction in dental anxiety at the 1-month and 3-month follow-ups. For moderation analyses, we will include a dummy variable for randomization arm, the potential moderator variable (distress tolerance or pain sensitivity), and an interaction term between the two (i.e. dummy variable multiplied by the mean-centered moderator variable). To maintain power to detect moderation, we will explore moderators

Page 18 of 28 Revision: May 12, 2023

separately. We will also use linear-mixed effects models in which we include potential confounding variables, as well as main effects and interaction terms of interest.

d) Withdrawal of Subjects

We do not expect that there will be much in the way of withdrawal during the dental anxiety intervention itself, although it is not entirely out of the realm of possibility. We expect that the major concerns will have to do with the assessments over time, and in that case, concerns over withdrawal are really concerns over retention. However, we note a few issues below.

Reasons for Withdrawal related to the Intervention

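### Secondary-scale equivalence between providers can be read as equal efficacy even on a scale that I-CBT has not been shown to change

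*Combined protocol and SAP*

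**What the plan says.** Section 8(c), Planned Analyses, Specific Aim 1: "Aim 1 will test the equivalence hypothesis (Ho: the two intervention conditions are not equivalent". The method follows: "The two one-sided tests (TOST) procedure of Schuirmann (1987) will be used to conduct the equivalence test". MDAS and ADIS fear are the primary outcomes, and mixed models are added. The same paragraph continues "Similar analyses will be conducted for secondary outcome measures (pain sensitivity index, anxiety sensitivity index, sleep disturbance and sleep-related impairment scales"; its list also takes in the disability scale, the distress tolerance scale, client satisfaction and blood-injury-injection phobia, eight scales in all. No equivalence margin is given for any scale.

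Analysis of Secondary Objectives asks whether Objectives 1 and 2 show up in related constructs, naming pain sensitivity, distress tolerance, anxiety sensitivity and "anticipated and perceived pain and anxiety, the statistical methods described above will be used". Objective 1 in section 4 is a comparison of efficacy between the two kinds of provider. The secondary objectives there say "We will examine whether I-CBT has similar effects on related measures".

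The measures section describes the PSI as follows: "Pain sensitivity is considered a stable characteristic that can influence the development of situational fears". It also says "The PSI will play a dual role in this study, as a secondary outcome measure and as a hypothesized moderator".

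Specific Aim 2 compares I-CBT with control, including on secondary measures, but lists those only by example. The CSQ-8 is collected from I-CBT patients only.

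**The concern.** Equivalence between two ways of delivering a treatment is evidence of equal efficacy on a scale only if the treatment moves that scale. If neither arm changes it, the arms agree whatever the quality of delivery. The plan has a control arm that can show whether a scale moved, but it does not link that contrast to the Aim 1 reading. The within-group change analysis in Aim 1 covers only dental anxiety and fear, so it does not fill the gap.

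The abstract says that showing roughly equal efficacy would help spread I-CBT to dental offices through dental assistants. Equivalence on secondary scales at one and three months could be listed as corroboration of that conclusion while saying nothing about it.

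**Working it through.** **The plan's own figure.** The only design figure is about 550 patients in three roughly equal arms: 550/3 = 183 per arm. It cannot be reproduced, because no margin, SD, effect size, power or planned dropout is given.

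**Inputs**
- n = 183 per arm (Recruitment Methods). With an assumed 20% loss, 183 × 0.8 ≈ 146.
- Overall significance level 0.05 (Specific Aim 1). The level of each one-sided test is not stated; 0.05 is used, with 0.025 as a variant.
- Baseline correlation r. The Missing Data section uses ANCOVA controlling for baseline. The only figure in the documents for any of these secondary scales is for the DTS, "adequate six-month test-retest reliability (r =.61"). It covers six months, so using it here is an assumption. The range runs from r = 0 (no adjustment) to r = 0.61.
- Margin m, in SD units of the follow-up score: assumed, 0.15 to 0.40.
- True provider difference: 0, which is what follows if I-CBT leaves the scale unchanged in both arms.

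**Formulas**

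SE = √[2(1 − r²)/n]

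P(TOST passes | difference 0) = 2Φ(m/SE − 1.645) − 1, set to 0 if negative

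**Standard errors at n = 183**
- r = 0: √(2/183) = 0.1045 SD
- r = 0.61: 0.1045 × √(1 − 0.3721) = 0.1045 × 0.792 = 0.0828 SD

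**Worked cases at m = 0.30**
- r = 0: 0.30/0.1045 − 1.645 = 1.225; 2Φ(1.225) − 1 = 0.78
- r = 0.61: 0.30/0.0828 − 1.645 = 1.977; 2Φ(1.977) − 1 = 0.95

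**Chance of declaring equivalence, one-sided 0.05**

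| Margin (SD) | n = 183, r = 0 | n = 183, r = 0.61 | n = 146, r = 0 | n = 146, r = 0.61 |
|---|---|---|---|---|
| 0.15 | 0% | 13% | 0% | 0% |
| 0.20 | 21% | 56% | 5% | 39% |
| 0.25 | 54.5% | 83% | 38% | 71% |
| 0.30 | 78% | 95% | 64% | 89% |
| 0.40 | 97% | 99.9% | 92% | 99% |

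With each one-sided test at 0.025 and n = 183, a 0.30 SD margin gives 64% to 90%. An ANCOVA simulation (n = 183, r = 0.61, 4,000 runs) gave 54%, 95% and 99.8% at 0.20, 0.30 and 0.40 SD, in line with the formula.

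**A check that does not start from a chosen margin.** A margin giving 80% power at zero difference is (1.645 + 1.282) × SE: 0.31 SD unadjusted, or 0.24 SD at r = 0.61. With such a margin for a scale, TOST also has an 80% chance of passing when I-CBT does nothing to that scale.

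**The case against.** Several points on the other side are sound.

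- **No margin, so no certain outcome.** A reader might infer that the arms would be declared equivalent on any unchanged scale. The documents do not support that. At 0.20 SD the chance is 21% unadjusted and about 39% with 20% loss at r = 0.61; at 0.15 SD it is 0% to 13%.
- **These percentages are not error rates.** They are TOST power at a true difference of zero. If the providers do not differ, saying so is right. The fault would lie in treating the result as equal efficacy.
- **TOST is not named for the secondary scales.** The carry-over phrase comes straight after sentences on mixed models. The Analysis of Secondary Objectives, which applies the methods above to Objective 1, makes TOST the natural reading but not an explicit one.
- **Only the PSI is called stable.** A reader might infer that all the secondary scales are uninformative. The disability scale was adapted to dental anxiety, the FQ-BII covers dental procedures, and the protocol hopes for improvement in sleep. A correlation of .61 for the DTS is moderate.
- **Aim 2 will supply comparisons with control.** A careful reader could see there that a scale had not moved.

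The last point does not dispose of the matter. The plan never ties those contrasts to the Aim 1 reading, and it examines the related constructs precisely to see whether the efficacy comparison carries over to them.

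**Conclusion.** The concern holds in a limited form. The Aim 1 methods extend to the secondary scales, and no shown effect of I-CBT on a scale is required before equivalence there can support equal efficacy. On a scale that I-CBT does not change, equivalence could be declared, and with a margin of about 0.3 SD or wider probably would be: 78% to 95% at 183 per arm, no dropout, one-sided 0.05, r from 0 to 0.61. At 0.2 SD the range is 21% to 56%. The margins are assumptions, and whether any given scale stays unchanged is a conditional premise, most plausible for the PSI.

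Two further inferences should be resisted. The primary MDAS and ADIS tests are not undermined. Nor does the lack of control data rule out a provider comparison on the CSQ-8: it measures satisfaction with the service delivered and compares directly between the two I-CBT arms.

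**What to change.** In Specific Aim 1, add that:

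- for the PSI, ASI-3, two PROMIS sleep scales, SDS, DTS and FQ-BII, equivalence counts as support for equal efficacy only where the Aim 2 contrast (both I-CBT arms pooled against control) on the same scale and at the same time point shows an effect in favour of I-CBT;
- the equivalence margin for each of these scales is fixed before analysis;
- otherwise, the between-provider difference is reported with its 90% CI beside the I-CBT versus control estimate and CI, with a statement that no I-CBT effect was shown, without claiming that none exists;
- the CSQ-8 is outside this condition.

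Aim 2 should name the seven scales, since its list is now by example. The condition is a minimum and not proof: the pooled contrast does not show that each provider arm moved the scale, and with many tests some contrasts will favour I-CBT by chance.

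The cost is wording, the choice of margins, and fewer secondary equivalence statements. Patients, procedures, sample size and the primary tests do not change.

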1) Abstract of the study

This protocol describes activities that are a part of a clinical trial grant (U01) application by the investigators to the National Institute of Dental and Craniofacial Research (NIDCR) examining an internet-based cognitive-behavioral treatment (I-CBT) for patients of the Temple University Kornberg School of Dentistry (TUKSoD) who suffer from significant dental anxiety. This is a 5-year clinical trial that will evaluate the efficacy of a brief I-CBT for the treatment of impairing dental anxiety among those seeking dental care at the clinics of TUKSoD.

The study will be a randomized controlled trial in which patients seeking services at the TUKSoD Faculty Practice Clinic who screen positive for dental anxiety will be provided with I-CBT under the supervision of psychology clinicians highly trained in CBT techniques versus dental assistants with minimal training designed specifically to prepare them to supervise the delivery of the I-CBT protocol to anxious dental patients. Patients (N=550) will be randomized to one of these two arms of the study or to a third (control) arm in which participants will be asked to view a video of nature scenes for a period of time equivalent to the dental anxiety intervention. The dental care provider for all participants will also be informed of their scores on the dental anxiety screening measure. Demonstration of relatively equivalent efficacy of the I-CBT treatment when provided by dental assistants versus more highly trained psychology personnel will facilitate the dissemination of I-CBT for dental anxiety to dental offices in a sustainable way that would allow greater access for a larger number of potential patients with dental anxiety.

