Initial assessments will be conducted in the few weeks preceding patients' already-scheduled appointments for dental treatment at TUKSoD. Patients meeting inclusion and exclusion criteria will then be offered I-CBT or the control intervention, to occur immediately prior to their scheduled dental treatment appointment. Efficacy based on primary outcome measures (e.g., reduction from baseline on self-rated and clinician-rated measures of dental anxiety/fear) and secondary outcome measures will be examined at assessments one and three months thereafter. Some additional interview ratings will be gathered from patients after they complete the dental anxiety intervention and after they complete the pursuant dental treatment appointment, and one brief questionnaire will be administered six and twelve months later. Finally, we will examine the impact that the intervention may have on attendance at scheduled dental appointments over the next 12 months.

2) Protocol Title

Efficacy of an Internet-based intervention for dental anxiety

3) Investigators

Page 1 of 28 Revision: May 12, 2023

[name], Associate Professor, Chair, and Residency Director, Pediatric Dentistry and Community Oral Health Sciences, Maurice H. Kornberg School of Dentistry, Temple University

[name], Assistant Professor, Department of Oral Health Sciences, Maurice H. Kornberg School of Dentistry, Temple University

4) Objectives

The primary goal of human subjects activities described in this protocol is to evaluate the efficacy of the Internet-based intervention for dental anxiety among patients presenting to the participating clinic(s). To achieve this overall goal, we propose 3 primary objectives:

Objective 1: We will compare the efficacy of I-CBT as administered by personnel with training and experience in CBT to the efficacy of the intervention as administered by dental assistants who have undergone a brief but specific training in the administration of the intervention, a goal which would allow the greater dissemination of this intervention. We will also examine within-group reduction of anxiety at assessments one and three months after the administration of the intervention.

Objective 2: We will compare the efficacy of the intervention, administered either by CBT personnel or dental staff, to an active control condition, the viewing of the control video and the notification of the dental provider of the patient's score on a measure of dental anxiety before the dental appointment.

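### The reduction part of Specific Aim 1 asks a causal question but answers it from within-arm change, with no contrast against the randomised control arm

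*Combined protocol and SAP*

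**What the plan says.** The first paragraph of Specific Aim 1 (section 8c, Planned Analyses) is an equivalence comparison of the two I-CBT arms. The second paragraph adds a separate question: "Aim 1 will also determine whether the Internet-based intervention reduces dental anxiety/fear as determined by self-ratings or assessor ratings", at one and three months. Two methods follow. The first is "Initially, we will assess within-group change of anxiety or fear scores for each condition separately using paired" t-tests. The second is: "Linear mixed-effects models will be used to estimate within-group reduction of anxiety/fear at assessments one and three months", adjusted for covariates. Neither compares an I-CBT arm with control.

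Section 4, Objective 1, describes the same analysis more mildly: "We will also examine within-group reduction of anxiety at assessments one and three months after the administration of the intervention". No sentence in the document calls the within-arm results descriptive or makes a conclusion of reduction depend on the control comparison.

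The design does include a control. The Abstract says patients may be randomised "to a third (control) arm in which participants will be asked to view a video of nature scenes", and Planned Analyses schedules the full battery at baseline, 1 month and 3 months for patients in all three conditions. The paragraph on Specific Aim 2 reads: "Aim 2 will assess the superiority hypothesis (Ho: there are no significant differences between the interventions and control". It uses the same two primary outcomes, the MDAS and the ADIS-5 fear rating.

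**The concern.** Whether an intervention reduces anxiety is a causal question. A before-after change within one arm answers it only if scores would otherwise have stayed level. Several features of this trial could lower scores in every arm whether or not I-CBT works:

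- Patients enter on a high MDAS (a total of 19, or at least two items scored 4 or 5), and the MDAS is a primary outcome, so some regression to the mean is possible.
- Baseline precedes a booked visit: "Initial assessments will be conducted in the few weeks preceding" the appointment. Follow-up comes one and three months after it.
- The dentist is told the patient's anxiety score in all arms, control included (Abstract; section 9, Active Control Condition).

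At stake is what may be concluded under a primary objective. If all arms fell together, a reader applying this paragraph as written could report that I-CBT reduces anxiety when it added nothing over the nature video. The two I-CBT arms falling by the same amount would also sit comfortably with a finding of equivalence, so Aim 1 does not itself expose the problem.

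**Working it through.** **The plan's own figure.** There is none to reproduce. The sample size of 550 is given without power, SD, effect size, margin or dropout, and no figure is attached to the within-group analysis. The check below asks how often the stated test declares a reduction when the treatment effect is zero.

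**Inputs from the document.** About 550 patients roughly evenly divided over three arms (Recruitment Methods), so 550/3 ≈ 183 per arm; significance at p < 0.05 (Specific Aim 1); MDAS range 5 to 25 and test-retest r = 0.82, with no retest interval stated (Initial Screening Measures).

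**Assumptions.** Two-sided testing; MDAS SD of 3 to 5; baseline-to-follow-up correlation of 0.5 to 0.82; the same mean fall in all three arms; no loss to follow-up.

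**Formulas.** SD of change = SD × √(2(1 − r)). The paired t-test is significant once the mean fall exceeds t(0.975, 182)/√183 = 0.146 SD of change. For a fall d, the chance of significance is about Φ(d√183/SD of change − t), plus a negligible opposite tail.

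**One case in full.** With SD 4 and r = 0.82, the SD of change is 4 × √0.36 = 2.4. The smallest significant fall is 0.146 × 2.4 = 0.35 points. For a 0.5-point fall, 0.5 × 13.53/2.4 = 2.82, and Φ(2.82 − 1.97) = 0.80.

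**Chance that one I-CBT arm shows a significant reduction with zero treatment effect:**

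| SD | r | SD of change | Smallest significant fall | Shared fall 0.25 | 0.5 | 1 |
|---|---|---|---|---|---|---|
| 3 | 0.82 | 1.8 | 0.26 | 46% | 96% | >99% |
| 3 | 0.5 | 3.0 | 0.44 | 20% | 61% | 99% |
| 4 | 0.82 | 2.4 | 0.35 | 29% | 80% | >99% |
| 4 | 0.5 | 4.0 | 0.58 | 13% | 39% | 92% |
| 5 | 0.82 | 3.0 | 0.44 | 20% | 61% | 99% |
| 5 | 0.5 | 5.0 | 0.73 | 10% | 27% | 77% |

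**Against the controlled contrast.** In 4,000 simulated trials per scenario, a two-sample t-test on change (I-CBT pooled, 2 × 183, against 184 controls) was significant in 4.5% to 5.7% of trials, in line with the nominal 5%. In the same runs, at SD 4 and r = 0.82, both I-CBT arms showed a significant within-arm fall in 64% of trials for a shared 0.5-point fall and in over 99% for 1 point.

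**What the controlled contrast can detect.** With 367 against 183, a difference of (1.96 + 0.84) × √(1/183 + 1/367) ≈ 0.25 SD has 80% power before loss to follow-up. In units of the 2.4-point SD of change that is 0.25 × 2.4 ≈ 0.6 points.

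**The case against.** The strongest reply is that the controlled test already exists and is primary. Aim 2 compares I-CBT with control on the same outcomes, with a mixed model as its main analysis. The Missing Data section specifies only between-arm contrasts, including the pooled I-CBT arms against control adjusted for baseline. Section 5 states the efficacy hypothesis as a stronger effect than the active control. A decline common to all arms would tend to appear as a null Aim 2. This stands. A reader might infer that ordinary decline would be reported as a treatment effect, or that the trial has no controlled test of efficacy. The documents support neither.

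A reader might also infer that part of Objective 1 would be met by drift alone. The plan sets no success criterion for within-arm change, Objective 1 speaks only of examining it, and the stated Aim 1 hypothesis is equivalence between two randomised arms.

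The mechanism is plausible but not established. MDAS items are hypothetical, so scores need not follow the pending visit. The MDAS is repeated at baseline after screening, so part of any regression to the mean may occur before the baseline value. Section 5 notes that invasive treatment can maintain or worsen anxiety, so even the direction of change after a visit is not certain. Nor does the test reject for almost any drift: at 0.25 points the chance is 10% to 46%.

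Finally, the paired tests apply to each condition separately. Since Planned Analyses speaks of three conditions, control-arm change may be intended too; the rest of Aim 1 concerns the two intervention conditions, so this is unclear. Even on the wider reading, separate tests in each arm are not a comparison between arms.

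What remains is the mismatch between a causal question and uncontrolled methods, with nothing in the text to stop the conclusion being drawn.

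**Conclusion.** The point holds as a defect of inference confined to the second paragraph of Specific Aim 1. As written, that paragraph lets a conclusion that I-CBT reduces anxiety or fear rest on change that a shared decline could produce. With no treatment effect, the chance of a significant reduction in one I-CBT arm is 27% to 96% for a shared fall of 0.5 points and 77% to 100% for 1 point, against about 5% for the comparison with control.

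These figures rest on the assumed SD, correlation and full follow-up, and on a decline whose size the documents do not give. Loss to follow-up would lower them somewhat: with an assumed 20% loss (146 per arm), the smallest significant fall rises from 0.146 to 0.164 SD of change. The Aim 1 equivalence test and the Aim 2 superiority test are not affected.

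**What to change.** State in Specific Aim 1 that any conclusion that I-CBT reduces dental anxiety or fear rests on the randomised comparison with control in Aim 2. In Aim 1, report within-arm change at 1 and 3 months for all three arms side by side, control included, as descriptive estimates with 95% confidence intervals. Do not use the paired t-tests as evidence that the intervention reduces anxiety. Bring the wording of the aim into line with Objective 1, which speaks of examining within-group change.

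The cost is a change of wording; the control arm's primary outcomes are already scheduled at both times. The downside is that Aim 1 loses a stand-alone claim of reduction.
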